5.10.4 Qualitative process evaluation

This feasibility study will focus upon understanding what might be seen as facilitators and barriers to implementation of the intervention to inform implementation of the intervention within a future definitive trial. Within these, we will consider seek to understand the *context* (how external factors influence the delivery and functioning of the interventions) and *implementation* (evaluation of the way in which the intervention is delivered, and the quality and quantity of the intervention delivered).

5.11 Criteria for Discontinuation

We will discontinue the treatment if the participant manifest they do not wish to continue with the intervention or study; the participant or facilitators (or researchers) believe that the intervention or trial participation will result in, or is likely to result in, a serious adverse reaction if continued; if the participant does not attend four consecutive group therapy sessions (they are made aware of this rule before starting).

5.12 End of Study Definition

The end of the study will be defined as after providing the programme to the control group, after their last 6 month follow up assessment which is part of our ethic responsibility.

6. STATISTICAL CONSIDERATIONS

6.1 Sample Size

60 participants (30 per group) will allow us to address the stated objectives of this feasibility trial. This represents recruitment to Bi-REAL at full capacity (10 per group), with equivalent numbers randomised to TAU. Previous studies with this population estimate an attrition rate of 17% (with respect to the primary end point at nine months post-randomisation. Our sample size of 48 will allow us to estimate this level of attrition for a future definitive trial with a precision of $\pm 15\%$ with 95% certainty.

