2. SUMMARY/SYNOPSIS

Short Title	BI-REAL: a 12-session DBT Skills Group Intervention adapted for Bipolar Disorder – a feasibility Randomized Pilot Trial
Methodology	Feasibility study with a two-arm randomised parallel controlled trial design
Research Sites	University of Coimbra - Center for Research in Neuropsychology and Cognitive and Behavioral Intervention (CINEICC)
Objectives/Aims	To assess the feasibility and acceptability of a future definitive randomised controlled trial (RCT) evaluating the feasibility and acceptability of a Dialectical Behaviour Therapy Skills intervention for adults with bipolar and related disorders
Number of Participants/Patients	60
Main Inclusion Criteria	
Client group: individuals with a Diagnosis of Bipolar and Related Disorders:
 
Inclusion criteria:
 
 i) aged 18 or over ii) lifetime diagnosis of Bipolar Disorder (I,II, "other specified bipolar disorder") or Cyclothymic Disorder, according to DSM-V iii) mood instability (at least one complete mood episode in the last 5 years, and reported interference of sub-clinical mood symptoms) iv) Sufficient competency in Portuguese to be able to complete study measures without the need for translation. v) Having access to means to participate in the online group (i.e. access to a stable internet connection, having a functional camera and microphone on their computer, and zoom) 
Exclusion criteria:
 
 i) current high risk of suicide (measured through clinical interview) ii) Bipolar disorder secondary to an organic cause; iii) Diagnosis of substance dependence or continuous illicit substance misuse resulting in uncertain primary diagnosis;

	iv) Acute episode of mania, hypomania or major depressive episode (at baseline) or not euthymic. v) Other high-risk pervasive disorders such as Borderline Personality Disorder; persistent self-injury; vi) the person lacks capacity to consent to treatment, low insight vii) Receiving psychological specific treatment for BD
Statistical Methodology and Analysis (if applicable)	Quantitative analysis: descriptive, linear mixed models Qualitative analysis: qualitative interview and questionnaire assessing programmes utility, acceptability and satisfaction
Proposed Start Date	01.02.2020
Proposed End Date	31.08.2022

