4. TRIAL AIMS

1. To inform the recruitment and timeline of a future fully powered trial by establishing the number of participants identified, approached, consented, randomised and completed.
3. To refine future trial procedures by establishing the acceptability and experience of the trial process to participants, including randomisation and completion of outcome measures.
4. To determine the optimal primary outcome measure in a future trial by assessing the performance of selected candidate primary outcome measures with respect to the level of acceptability to participants (completion rates) and participant-perceived relevance and value, and based on some additional secondary measures that are thought to improve with DBT-ST.
5. To inform estimation of sample size for a future trial by measuring data completeness at follow-up (participant attrition).
7. To further assess the acceptability of the treatment via qualitative interviews and, based on input from trial participants and clinicians, to further refine and develop the treatment manual and the procedures for training trial therapists.

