5. METHOD

5.1 Research Design

Our feasibility study is a two-arm randomised parallel controlled trial design: where we intend to have 60 participants that will be randomised on a 1:1 ratio to Treatment as Usual (TAU) [control arm] or Bi-REAL programme plus TAU (TAU + Bi-REAL) [intervention arm]. Outcome measures will be recorded at baseline and at post-intervention (3 months after baseline) and with a follow-up point at 3 months after treatment ends (6 months post-randomisation). See appendix 1 for more detail.

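### Section 6.1 plans 60 participants but gives its precision for an unexplained sample of 48, and ±15% at 17% attrition fits neither 48 nor 60 in total

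*Combined protocol and SAP*

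**What the plan says.** Section 6.1 opens with the planned size: "60 participants (30 per group) will allow us to address the stated objectives of this feasibility trial". It justifies that number by group capacity: "This represents recruitment to Bi-REAL at full capacity (10 per group), with equivalent numbers randomised to TAU". It then gives the planning value, "Previous studies with this population estimate an attrition rate of 17% (with respect to the primary end point at nine months post-randomisation", and closes with the precision claim: "Our sample size of 48 will allow us to estimate this level of attrition for a future definitive trial with a precision of" ±15%, at 95% confidence.

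The other statements of sample size agree on 60. The synopsis entry headed "Number of Participants/Patients" gives 60, and section 5.1 says "we intend to have 60 participants that will be randomised on a 1:1 ratio". Section 5.1 also places the last assessment at "a follow-up point at 3 months after treatment ends (6 months post-randomisation").

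Attrition matters because of aim 5 in section 4: "To inform estimation of sample size for a future trial by measuring data completeness at follow-up (participant attrition"). Section 6.2 plans to report attrition descriptively.

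**The concern.** The precision sentence names a sample size that is not the planned one. The number 48 appears nowhere else as a sample size and is not derived. The sentence also leaves open whether ±15% is for the trial as a whole or for one arm, and which interval method was used. A reader therefore cannot tell which design the error bar belongs to.

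This is the plan's only statement of how precisely it will estimate attrition, and aim 5 feeds that estimate into the size of a future trial. If the figure belongs to a different N, or to one arm when the reader takes it as overall, the uncertainty carried forward will be misjudged.

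**Working it through.** **Inputs.** Attrition p = 0.17, 95% confidence and stated half-width 0.15 (section 6.1). Stated n = 48 (section 6.1). Planned n = 60, 30 per arm (section 6.1, synopsis, section 5.1).

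**Step 1: the plan's figure as written.** The normal-approximation half-width is 1.96 × √(p(1 − p)/n), with p(1 − p) = 0.17 × 0.83 = 0.1411.

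- n = 48: 1.96 × √(0.1411/48) = 0.106, or ±10.6 points. The stated ±15 is not reproduced.
- n = 60: 1.96 × √(0.1411/60) = 0.095, or ±9.5 points. It is not reproduced here either.

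**Step 2: the n that gives ±15.** n = 1.96² × 0.1411 / 0.15² = 24.1. So ±15 corresponds to 24 people, which is one arm of a 48-person trial.

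**Step 3: sensitivity to the interval method.** 95% half-widths in percentage points at 17%. The exact (Clopper-Pearson) column uses the nearest whole count and averages the two sides.

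| n | Normal | Continuity-corrected | Wilson | Agresti-Coull | Exact, mean |
|---|---|---|---|---|---|
| 24 (one arm of 48) | 15.0 | 17.1 | 14.7 | 15.3 | 16.3 (4/24) |
| 30 (one arm of 60) | 13.4 | 15.1 | 13.2 | 13.7 | 14.5 (5/30) |
| 48 in total | 10.6 | 11.7 | 10.5 | 10.8 | 11.4 (8/48) |
| 60 in total | 9.5 | 10.3 | 9.4 | 9.6 | 10.1 (10/60) |

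No method brings 48 or 60 in total near 15. Even with the worst case p = 0.5, the normal approximation gives ±14.1 for 48 and ±12.7 for 60. Adding a continuity correction at p = 0.5 and n = 48 gives ±15.2, but the sentence refers to the 17% level.

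**Step 4: asymmetry of the exact intervals.**

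- 10/60 (16.7%): 8.3% to 28.5%, which is 8.4 points below and 11.9 above.
- 5/30 (16.7%): 5.6% to 34.7%, which is 11.0 points below and 18.1 above.

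**Step 5: is 48 the number expected to remain?** 60 × 0.83 = 49.8, not 48. Retaining 48 of 60 would need 20% attrition (60 × 0.80 = 48), which the plan does not state. In any case the denominator of an attrition rate is the number randomised, not the number who complete.

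**The case against.** The strongest reply is that 48 is shown to be unexplained, and the ±15% may be loose rather than false.

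- **Routes to 48.** Per arm, 30 × 0.83 = 24.9, cut down to 24 and doubled, gives 48, and 24 per arm yields ±15.0. This is possible, but it needs truncation, a completer denominator and a per-arm basis, none of which the plan states.
- **A per-arm reading for the planned 30.** A continuity-corrected interval (±15.1) or an exact one (mean 14.5) rounds to about 15. This reading cannot be excluded. It would still leave 48 as the wrong number, with arm and method unstated.
- **±15 as an upper bound.** Both totals do better than ±15, so the overall claim is not optimistic. That stands for the trial as a whole. Per arm it holds less well: if exact limits are used, the upper limit lies about 18 points above 5/30.
- **No decision depends on it.** This stands. The criteria in section 4.1 use no confidence interval. The third asks for 3-month follow-up data from at least 60%. At 17% attrition retention is 83%; taking off 15 points leaves 68%, and the exact per-arm upper limit of 34.7% attrition still leaves 65.3%.

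These points limit the consequence. None makes the sentence correct for the trial that is planned.

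**Conclusion.** The concern holds and is minor. Section 6.1 is wrong as written: its precision statement uses 48 where the plan is 60, and ±15% is the half-width for neither number in total. For the planned 60, the normal approximation gives ±9.5 points overall, so the stated figure is 5.5 points too wide on that reading. It gives ±13.4 for each arm of 30. Across the five methods the ranges are 9.4 to 10.3 overall and 13.2 to 15.1 per arm.

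The likeliest origin is a per-arm calculation for a 48-person design that was not updated, but that is an inference and the conclusion does not depend on it. The figures assume the plan's own 17%. That value is tied to nine months, whereas this trial's last assessment is at 6 months, so it is a planning value only.

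**What to change.** Replace the last sentence of section 6.1, and with it the 48, by wording such as:

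> With 60 randomised, and using 17% attrition as a planning value (taken from a nine-month figure in previous studies; this trial's last assessment is at 6 months post-randomisation), the 95% CI half-width is about ±9.5 percentage points overall and ±13.4 per arm of 30 (normal approximation; exact intervals about 8% to 29% for 10/60 and 6% to 35% for 5/30).

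If the sponsor intended 48 to mean something else, such as a minimum number with follow-up data, that should be defined separately and not used as the denominator for attrition. The cost is one sentence of protocol text. It needs no more patients and no change to the analysis.

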6.2 Method of analysis

Given the feasibility objectives of this study, the initial focus of data analysis will be descriptive, regarding the enrolment data, attrition rates and treatment and study dropout. We will also describe the acceptability of the programme though the report of the programme assessment questionnaire and interview, along with the scores of the GSRS. The number of people completing the intervention will be reported and it is defined as attending at least 65% of group sessions, which corresponds to 8 sessions approximately). We will also report on the number who complete the research outcome measures alongside means and standard deviations regarding the number, length and frequency (time between) of sessions. All protocol deviations, along with reasons and number of missing items on questionnaires will be reported.

To address the other primary outcome (i.e., recovery and QoL) and informing future sample size estimation) levels of completion and mean and standard deviations (or equivalent) for all outcomes for both study arms will be reported at baseline, three and six months follow up, as will participant

rankings of personal value and relevance of clinical outcome measures. Additionally we expect to do linear mixed models analysis to explore the time x group interaction in the variables in study.

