This study aims to investigate if our programme Bi-REAL (Respond Effectively and Live mindfully), a 12-session online DBT skills intervention for BD, is acceptable and feasible and if it shows preliminary improvements in selected variables connected to recovery and emotional regulation and other psychological processes, in a randomised controlled pilot trial.

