4.1 General aims

We will also evaluate whether the following criteria have been met prior to planning a future definitive trial:

1. Trial participation does not lead to serious negative consequences (unexpected adverse reactions) for our participants.
2. Any serious concerns about the acceptability and feasibility of the trial procedures can be rectified prior to a full trial.
3. Follow-up data at 3 months is available from at least 60% of participants.
4. At least 60% of patients complete treatment (attend at least 50% of possible sessions).

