7. ETHICS

7.1 The intervention

Particular caution and attention must be taken when administering a new therapeutic intervention to monitor any potential negative reactions. Although psychological interventions generally have minimal harmful effects, there is still a slight risk involved. The skills training we developed is however based on a well-established treatment (DBT), and it has been adapted and used in BD, with no adverse reactions reported, and with good acceptability (Eisner et al., 2017; Goldstein et al., 2015; Van Dijk et al., 2013). Nevertheless, more robust studies are still needed, since most of these studies were pilots as well. Our programme seeks to follow the same principles, with some additional innovations, namely with specific skills to help upregulate and down regulate emotions in depressive/hypo/manic periods. If at any period a potential ethical issue arises from delivery of the treatment, the participants will be approached, and risk protocol will be put into place (according to the place where they are routinely followed). Information provided by participants as part of their treatment will be treated in confidence. Participants will be informed of the circumstances under which confidentiality may be broken and will be consulted with as far as possible if this should become necessary.

In addition, regarding the group session, a set of "ground rules" will be established at the pre-session, together with the facilitators. All group participants will be made aware that they should not divulge what is talked in the group, and at the same time they do not have to share any information in the group that they do not wish to. Due to the training approach and format of the group, which is not the same as a traditional therapeutic group, participants can discuss the material and exercises without having to share personal information if they do not wish to.

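### Section 6.2 does not say how baseline enters the exploratory mixed model; read in the ordinary way it compares changes from baseline, which is unbiased but less precise than adjusting for baseline (minor)

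*Combined protocol and SAP*

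**What the plan says.** Section 6.2 puts description first: "the initial focus of data analysis will be descriptive". For the outcome scales it promises that "mean and standard deviations (or equivalent) for all outcomes for both study arms will be reported at baseline, three and six months follow up". It then adds one modelling sentence: "Additionally we expect to do linear mixed models analysis to explore the time x group interaction in the variables in study". The synopsis lists linear mixed models without further detail.

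No section states whether baseline is a response or a covariate, whether the arms share a baseline mean, how time is coded, or which covariance structure or covariates are used.

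Section 5.1 and Appendix 3 schedule the outcome scales at baseline, at the end of treatment (3 months) and at 6 months. Section 5.8 places randomisation after the baseline assessment.

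**The concern.** Section 3 says that the trial will look at "if it shows preliminary improvements in selected variables connected to recovery and emotional regulation and other psychological processes", and section 5.10.1 names recovery and quality of life as primary outcomes. The sentence in 6.2 is the only planned comparison of the arms on them.

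In routine use, a mixed model with a time x group term takes baseline as the first level of time and lets each arm have its own baseline mean. The interaction then subtracts each arm's observed baseline mean from its follow-up mean. In a randomised trial the expected baseline means are equal, so estimating their difference and subtracting it in full adds noise that adjustment would avoid.

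At stake is interval width. With 30 per arm the intervals will be wide in any case, and on this reading they would be wider than the data already collected require.

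**Working it through.** **No plan figure to reproduce.** The documents give no effect size, SD, power or precision for this model, and no baseline-to-follow-up correlation (rho).

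**Inputs from the documents**
- 30 per arm, 1:1 (6.1); measurements at baseline, 3 and 6 months (5.1, 6.2).
- Follow-up of 25 of 30 per arm, as an illustration. Section 6.1 says that previous studies "estimate an attrition rate of 17% (with respect to the primary end point at nine months post-randomisation", and 30 x 0.83 = 24.9. That horizon is nine months, whereas this trial stops at six.
- Follow-up of 18 of 30 per arm, from the criterion in 4.1: "Follow-up data at 3 months is available from at least 60% of participants" (30 x 0.60 = 18).

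**Assumptions:** rho from 0.3 to 0.9; SD 1 at every visit; the same correlation between all visits; data missing at random.

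**Step 1: what the interaction estimates.** A mixed model with three categorical times and group was fitted to one simulated complete data set. It gave interaction coefficients of -0.467 and -0.683, equal to the between-arm differences in mean change from baseline.

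**Step 2: variances.** Let n be the number per arm at baseline and q the fraction followed up. Per arm:
- separate baseline means (change contrast): (1 - rho^2)/(qn) + (1 - rho)^2/n
- one common baseline mean, or baseline as covariate with known slope: (1 - rho^2)/(qn)

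The variance ratio is 1 + q(1 - rho)/(1 + rho). At rho 0.5 and q = 25/30 this is 1 + 0.833 x 0.5/1.5 = 1.278, and sqrt(1.278) = 1.130, so the SE is 13% larger.

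| rho | SE excess, complete data | Variance ratio, 25/30 | SE excess, 25/30 | Variance ratio, 18/30 | SE excess, 18/30 |
|---|---|---|---|---|---|
| 0.3 | 24.0% | 1.449 | 20.4% | 1.323 | 15.0% |
| 0.5 | 15.5% | 1.278 | 13.0% | 1.200 | 9.5% |
| 0.7 | 8.5% | 1.147 | 7.1% | 1.106 | 5.2% |
| 0.8 | 5.4% | 1.093 | 4.5% | 1.067 | 3.3% |
| 0.9 | 2.6% | 1.044 | 2.2% | 1.032 | 1.6% |

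**Step 3: interval width at 25 of 30.** With t on 48 df, the 95% half-widths (change contrast v baseline-adjusted, slope known) are 0.65 v 0.54 SD at rho 0.3, 0.56 v 0.49 at 0.5, and 0.435 v 0.406 at 0.7.

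**Step 4: cost of estimating the slope.** The variance factor is 1 + 1/(N - 4). With N = 50 it is 1 + 1/46 = 1.022, or about 1% on the SE. Simulation (40,000 runs, 30 per arm at baseline and 25 followed up) gave variance ratios with the slope estimated of 1.42, 1.24 and 1.12 at rho 0.3, 0.5 and 0.7. The SE saved is 1 - 1/sqrt(ratio): 16.1%, 10.2% and 5.5%. At rho 0.8 and 0.9 the formula gives ratios of 1.093/1.022 = 1.069 and 1.044/1.022 = 1.022, so savings of about 3% and 1%. No estimator showed bias.

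**The case against.** The strongest reply is that nothing in 6.2 is wrong. A model with one baseline mean for both arms also has a time x group term, so the sentence permits the more precise analysis. The loss arises only if the team fits the other version. That stands: the text is under-specified, and it does not commit the team to a change analysis.

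Second, the size rests on a correlation that the documents do not give. If the scales are stable over three to six months and rho is 0.8 or more, the SE excess at 25 of 30 is 4.5% or less and the slope takes back about 1%. That stands too, and is why the range runs to 0.9. Adjustment stops paying only when 0.833 x (1 - rho)/(1 + rho) falls below 1/46, which is above a rho of about 0.95.

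Third, the model is an addition to a descriptive feasibility analysis. This also stands, and it sets the weight of the point.

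A reader might infer something stronger: that the planned comparison is biased or invalid. The documents do not support that. Baseline precedes randomisation (5.8), so the change contrast has the right expectation. With dropout, both approaches need data missing at random and a suitable covariance model. Nor do the documents support the inference that a feasibility conclusion is affected. The criteria in 4.1 concern adverse reactions, rectifiable procedural problems, follow-up completeness and treatment completion. The future sample size is to be informed by attrition (section 4, aim 5) and by descriptive means and SDs (6.2).

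**Conclusion.** The point holds as a minor one. Section 6.2 leaves open how baseline is used, and the usual way of fitting the model it names gives up precision that is available at almost no cost. At 25 of 30 per arm the change-contrast SE is about 20% larger at rho 0.3, falling to about 2% at 0.9. At the 60% follow-up threshold in 4.1 the range is 15% to under 2%. These figures assume equal variances and equal correlations over time. Unequal variances would alter the size of the loss, but in large samples the change contrast is never the more precise of the two. The consequence is a missed gain in an exploratory analysis; no stated sample size, power or progression decision changes.

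**What to change.** State one model in 6.2. For each outcome, fit a linear mixed model to the 3- and 6-month values with arm, visit as a categorical factor, arm x visit and the baseline value of that outcome, and name the covariance structure. Equivalently, keep baseline as a response with one mean common to both arms. Choose one of the two, and report the arm difference at 3 and at 6 months with a 95% interval, labelled exploratory.

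Say also which term carries the effect. In the covariate version it is the arm difference at each visit; arm x visit there asks only whether that difference changes between 3 and 6 months. In the common-mean version, with baseline as the reference time, the time x group terms at 3 and 6 months are themselves the arm differences, which stays closest to the present wording.

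The cost is two or three sentences and about 1% of the SE for the estimated slope. No new data are needed.
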